6.1 Study treatment

Hydroxytyrosol will be administered at 25 mg oral daily.

All dosages prescribed and dispensed to the patient and all dose changes during the study must be recorded.

Each bottle will contain 90 capsules. Each capsule will contain 250 mg of Hytolive powder (containing 25 mg of hydroxytyrosol). Medication labels will comply with US legal requirements and be printed in English. They will supply no information about the patient. The storage conditions for Hydrotyrosol will be described on the medication label.

Hydrotyrosol is supplied by PLThomas & Co, Inc. Hydrotyrosol is formulated as capsules for oral administration of 25mg, Capsules

6.1.1 Dosing regimen

The investigator should promote compliance by instructing the patient to take the study drug exactly as prescribed and by stating that compliance is necessary for the patient's safety and the validity of the study. The patient should be instructed to contact the investigator if he/she is unable for any reason to take the study drug as prescribed.

Hydroxytyrosol should be administered orally once daily at the same time every day, either consistently with or consistently without food

Capsules

The capsules should be swallowed whole with a glass of water and should not be chewed or crushed.

If vomiting occurs, no attempt should be made to replace the vomited dose. Patients should be instructed that if they miss a dose on one day, they must not take any extra dose the next day, but instead to immediately contact the study center as soon as possible to ask for advice.

6.2 Dose modifications

6.2.1 Dose modification and dose delay

If the participant develops grade 1 or 2 toxicities that are felt to be possibly, probably or definitely related to the study drug, the participant may go on a drug holiday (for no longer than 12 consecutive weeks) and restart the drug at the same dose. In each of these cases, the follow-up mammograms, breast biopsies will still be collected as per protocol one year after the initial start date of the intervention.

6.2.2 Visits

Before the drug start, the participants will have a general physical exam including a clinical breast exam, (with consent), height, weight, medical history, abdominal circumference, blood tests (CBC, CMP, fasting lipid panel), and a bilateral mammogram (if one not available within 90 days of registration). Breast MRI images will be collected and reviewed if available. If the mammogram is read as normal or benign, participants will undergo a non-directed core needle biopsy within 30 days of signing consent. For subjects who have taken an anticoagulation within the past 7 days, INR (International Normalized Ratio) must be $\leq 1.5 \times$ institutional upper limit of normal and Prothrombin Time and Partial Thromboplastin Time \leq IULN prior to the breast biopsy. If the patient has had a bone density (within the past 1 year) than it will be collected. Participants will then receive oral hydroxytyrosol for 1 year. A six month supply of study drug will be dispensed at Day 1 and another 6 months sample on month 6 visit. Participants will complete the self-administered FACT ES score at baseline, 6 months as well as at 12 months (Form ES).

6.2.2.1 Follow Up(s)

For follow-up visits, the participant will be seen at the study site at Months 3, 6 and 12. Follow-up assessments are based from the date of treatment start. Clinic visit should occur on Days 90, 180 and 360 (+/- 14 days for each assessment) to allow flexibility in scheduling. During these visits, counts of capsules will be recorded on the Treatment Form and in the participant's medical record. At month 13, the patient will receive a phone call for toxicity check.

Reported side-effects will also be assessed during these visits. Physical and clinical breast exam will be done at Months 3, 6 and 12. In addition, blood (CBC, CMP, fasting lipid panel) will be collected to monitor for toxicity at baseline, 3,6 and 12 months (see Study Calendar). Pill dispensing will be done at baseline and the Month 6 visit.

6.2.2.2 Drug Completion Visit (Month 12; Day 360 +/- 14 days)

After the 12 month intervention, all participants will have a complete physical exam including clinical breast exam. Once the participant completes the study drug, she should have the bilateral mammogram and biopsy scheduled within 4 weeks of stopping the intervention. If a subject has a breast MRI, the images will be collected. Participants will complete the self-administered Patient Questionnaire (FACT ES) at the completion of the treatment.

6.2.2.3 Compliance

The investigator/designee will count remaining unused hydroxytyrosol at each visit to assess compliance. A study medication log is provided in the CRF to capture subject compliance. If the subject forgets to return unused hydroxytyrosol at a scheduled visit, compliance will be confirmed by direct questioning of the subject. Subjects should be instructed to record any missed doses of hydroxytyrosol.

Compliance with hydroxytyrosol will be calculated by the ratio of number of pills actually taken to the number of pills that should have been taken. Compliance will be defined as a ratio ≥ 0.75 . Subjects with ratios between 1.00 and 0.75 will be allowed to continue on study. The importance of compliance with study medication should be reinforced to subjects with a ratio of less than 1.00. Subjects who have ratios < 0.75 will be taken off study for non-compliance.

Compliance with hydroxytyrosol will be evaluated by a physical pill count. In the event that the patient forgets to bring unused drug/empty drug bottles to the study visit, patients will be queried by study staff regarding compliance.

6.2.2.4 Post Intervention Follow Up Phone Call (Month 13; Day 390 +/- 7 days):

Participants will be called for assessment and/or resolution of adverse events.

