6.2.2.8 Criteria for Removal from Protocol Treatment

- a. Evidence of any cancer at any time, including DCIS. If the pathologic review of the baseline core needle breast biopsy confirms invasive breast cancer, the participant must be removed from protocol treatment.
- b. Unacceptable toxicity (as defined in Section 8.0).
- c. A participant who becomes pregnant while on treatment will be removed from protocol treatment since hormonal changes affect mammographic density.
- d. Delay of study intervention > 12 consecutive weeks due to any reason.
- e. Completion of twelve months of study intervention.
- f. The participant may withdraw from the study at any time for any reason.
- g. All reasons for discontinuation of the intervention must be documented in the Off Treatment Notice – Prevention Studies.
8. All participants will be followed for 13 months after registration. After 13 months, no further follow-up is required.
9. Non-compliance with study drug.

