6.2.2.9 Withdrawal from Protocol Treatment

Follow-up visits will continue even if the participant goes off study intervention early unless there is a withdrawal of consent.

7 Visit schedule and assessments

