7.2 Assessment types

Followup visits can occur (+/- 14 days for each assessment) to allow flexibility in scheduling. Follow-up visits will continue even if the participant goes off study intervention early. Risk assessment using Gail risk model if no known history of DCIS or LCIS and no deleterious mutation in BRCA 1 or 2, PTEN or P53. On months 3, 6, and 12 and 13 (Days 90, 180, 360 and 390 (+/- 14 days for each assessment)) adverse events will be noted. On months 3, 6, and 12 (90, 180, 360 +/- 14 days for each assessment), participants will be seen at the study sites to review the intake calendar which will document drug compliance and date of last menses. PT/PTT/INR required if the patient has been on anticoagulation during the past 7 days. FSH only to be performed if menopausal status needs to be determined (e.g. in patient with hysterectomy with at least one ovary intact). Mammogram within 90 days of registration. Bilateral Breast MRI will not be performed specifically for this study but if the images available within the past 90 days, they will be collected. Bone density not to be ordered specifically for the study and if not available does not exclude the patient from participating. The random core needle biopsy is mandatory for study participation. A six month supply of the study drug will be dispensed at Day 1 and at 6 months. The Fact ES questionnaire will be given at baseline, 6 months and at 12 months.

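### Section 6.2.2.3 takes women with a pill ratio below 0.75 off study, while other sections continue their follow-up; followed literally, it would leave a compliance-selected primary proportion

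*Combined protocol and SAP*

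**What the plan says.** Section 6.2.2.3 sets a compliance threshold of 0.75 for the ratio of pills taken to pills due. Above it, "Subjects with ratios between 1.00 and 0.75 will be allowed to continue on study". Below it, "Subjects who have ratios < 0.75 will be taken off study for non-compliance".

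Other sections treat the same event differently:

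- Section 6.2.2.8 is headed as criteria for removal from protocol treatment. Its list includes "Non-compliance with study drug" and, in the same list, "All participants will be followed for 13 months after registration".
- Section 6.2.2.9 says "Follow-up visits will continue even if the participant goes off study intervention early unless there is a withdrawal of consent". Note 1 to Table 7-1 repeats this, and Section 7.2 says it without the consent exception.
- Table 7-1 schedules the bilateral mammogram before study and at month 12, with no compliance condition.

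Two further places deal with the final mammogram. For toxicity-related drug holidays, Section 6.2.1 says "In each of these cases, the follow-up mammograms, breast biopsies will still be collected as per protocol", one year after the start date; the Safety Criteria in Section 5 say the same and also cover toxicity-related discontinuation. For women who finish, Section 6.2.2.2 says "Once the participant completes the study drug, she should have the bilateral mammogram and biopsy scheduled within 4 weeks of stopping the intervention". Neither mentions a woman stopped for non-compliance.

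Section 9 defines the primary endpoint as a responder proportion at one year, tested within each menopausal group against a null rate of 25%. It names no analysis set and gives no rule for a woman without a month-12 density.

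**The concern.** The two sentences in Section 6.2.2.3 contrast staying on study with coming off study, so a site could reasonably read the second as the end of participation, outcome imaging included. The protocol states outright that the one-year mammogram is kept after toxicity and gives no matching statement for non-compliance.

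At stake is which women supply the primary endpoint. Compliance is observed after baseline and may be related to density change or to other features of the women. If the mammogram is lost because of compliance, the reported proportion describes only women who kept taking the capsules. In a randomised trial the same rule would also act on the control arm and might partly cancel. Here the comparison is with a fixed 25%, so nothing offsets the selection. Because Section 9 is silent on the analysis set and on missing densities, it does not repair the loss, and a mammogram not taken at one year cannot be obtained later.

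**Working it through.** **Step 1. The instructions for a woman below 0.75, side by side**

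| Place | What happens to her |
|---|---|
| 6.2.2.3 | Taken off study |
| 6.2.2.8 | Removed from protocol treatment; all participants followed for 13 months |
| 6.2.2.9 and Table 7-1 note 1 | Visits continue after early stopping unless consent is withdrawn |
| 7.2 | Visits continue after early stopping |
| Table 7-1 | Month-12 mammogram, no compliance condition |
| 5 (Safety Criteria) and 6.2.1 | One-year mammogram kept, toxicity cases only |
| 6.2.2.2 | Mammogram after completing drug; early stoppers not addressed |

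The first row, read literally, cannot be carried out together with rows two to five.

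**Step 2. Who could be lost**

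Pills are counted at months 3, 6 and 12 (Sections 6.2.2.1 and 6.2.2.3, Table 7-1). A woman found below 0.75 at month 3 or 6 would leave before her mammogram falls due. A woman first found below 0.75 at month 12 has reached the visit at which it is scheduled and may still be imaged. The exposure is therefore mainly the month-3 and month-6 detections.

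**Step 3. Size of the selection effect**

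Let *d* be the share removed, *c* the response rate in the women retained and *q* the rate in those removed. The rate in all treated women is (1 − *d*)*c* + *dq*, so

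retained rate − all-treated rate = *d*(*c* − *q*).

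The documents give no value for *d* or for *c* − *q*. With assumed values:

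- *d* = 10%, difference 10 points: 0.10 × 0.10 = 0.01, or 1 point.
- *d* = 20%, difference 20 points: 0.20 × 0.20 = 0.04, or 4 points.
- Difference zero: no bias at any *d*.
- If the removed women respond more often, the sign reverses.

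For scale, the standard error of a 45% proportion in 50 women is √(0.45 × 0.55 / 50) = 0.070, or 7 points.

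**Step 4. Effect on the test against 25%**

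Suppose the rate in all 50 treated women in a group is exactly 25% and the removed women respond at 10% (assumed). The cut-off is the smallest count with an upper-tail probability of at most 0.025 under 25%.

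- 10% removed: retained rate (12.5 − 0.5)/45 = 26.7%. With a cut-off of 18 of 45, the upper-tail false-positive probability rises from 0.019 to 0.036.
- 20% removed: retained rate (12.5 − 1.0)/40 = 28.75%. With a cut-off of 17 of 40, it rises from 0.012 to 0.044.

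These show what the rule could do under one adverse assumption. They are not estimates for this trial.

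**Step 5. The plan's own power figure**

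For 45% against 25%, 50 women per group and two-sided 5%, the arcsine approximation gives Φ(2[arcsin√0.45 − arcsin√0.25]√50 − 1.96) = 0.849, which matches the stated 85%. Nothing in this point disputes that figure.

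**The case against.** The best reply is that a single loose phrase stands against a consistent rule. Section 6.2.2.8 names non-compliance and places it under removal from treatment. Continued follow-up is stated in four places, and where an exception is given it is withdrawal of consent. On that reading, off study means off study drug, and no mammogram is lost. This largely stands: it is the more natural reading of the whole document. It does not remove the conflict, because the section a site consults when it counts pills is the one that says otherwise, and no passage expressly preserves the non-complier's mammogram as the toxicity passages do.

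A second reply is that the bias is assumed. That stands in full. Its direction and size cannot be derived from the documents, and under the assumptions in the working it lies within one standard error, in a study described as a pilot.

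A reader might also infer that the 85% power is wrong or must be restated. The documents do not support that. The figure reproduces, and any lower figure needs a loss rate that the documents do not give, or the assumption that 45% is a rate for compliers only. Section 9 says only that the rate is based on published data. Attrition is a separate topic.

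**Conclusion.** The contradiction is real and should be corrected, but it is a conditional risk. If Sections 6.2.2.8, 6.2.2.9 and 7.2 and Table 7-1 govern, the risk largely disappears. If Section 6.2.2.3 is followed literally, women found non-compliant at month 3 or 6 lose their outcome and the primary proportion comes from a compliance-selected subset with no control arm to offset it.

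Two stronger readings should be resisted. One is that the plan definitely excludes non-compliers from the primary result; most of the text points the other way. The other is that the response rate will be inflated; that requires non-compliers to respond less often, which the documents do not establish.

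What is certain is that the instructions conflict and that Section 9 does not define the analysis set. The 1 to 4 point range rests wholly on the assumed shares and response differences.

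**What to change.** Reconcile Section 6.2.2.3 with Sections 6.2.2.8, 6.2.2.9 and 7.2 and Table 7-1, so that non-compliance does not end outcome collection and the month-12 mammogram already scheduled is still obtained unless consent is withdrawn. When drug is stopped is not at issue and need not change.

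In the Statistical Analysis part of Section 9, state that the primary proportion in each menopausal group includes all treated women with a month-12 density, regardless of compliance. Add two sensitivity analyses: the proportion among compliant women only, and the proportion with a missing month-12 density counted as non-response. No change to the power statement is needed for this point.

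The cost is a wording amendment and a few mammograms that Table 7-1 already requires. The observed response rate may also be lower if non-compliers are kept and respond less often.

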6.2.2.5 Biopsy Procedures

Participants will undergo core needle biopsy of normal breast tissue and the entire specimen will be submitted in total to research. The patient will not receive any results of the biopsy. Which breast to sample for biopsy will be at the discretion of the treating physician. This biopsy will not be directed at a particular lesion, but instead will be directed to the upper outer quadrant of the breast, which is typically a dense region of the breast. Core needle biopsy of the breast will be performed using a 14-gauge needle. After providing local anesthesia, a small skin incision is made in the breast and the core needle inserted. Up to four core biopsies are taken through this single incision, and after completing the biopsies, the wound is steri-stripped, dressed, and ice is placed on the wound to minimize bruising and scarring. The participant is encouraged to keep ice on the biopsy site for up to 2 hours. Part of the breast biopsy specimen will be saved as frozen tissue and other part will be placed in fixative for H & E and immunohistochemical staining for biomarkers. Potential complications include bleeding, pain, hematoma formation and bruising, or infection. The first biopsy will be before beginning hydroxytyrosol and the second biopsy will be done after treatment with hydroxytyrosol for one year. There will be no attempt to biopsy the exact same area of the breast or the same on the second breast biopsy. Instead, the upper outer quadrant of the breast will again be sampled.

Breast tissue can be collected from a scheduled biopsy or surgery and used in place of the breast biopsy.

Rationale for Mandatory Biopsy before and after the treatment with hydroxytyrosol.

Identifying risk biomarkers in benign breast tissue may provide direct measure of the effect of treatment on target tissue beyond any information imaging can provide. Ki-67 expression in benign breast tissue has been included into many early phase chemoprevention trials[34,35]. Unfortunately there are many limitations of using Ki67 expression in benign tissue (due to very low baseline Ki67 in these patients) and other tissue biomarkers are necessary. Therefore biopsy including markers for apoptosis, stem cell as well as Wnt Pathway (primary action of hydroxytyrosol) is proposed. Ki-67 expression does not have correlation with mammographic density therefore it is possible for the patient to have tissue changes but not able to detect it in the mammogram[36].

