8.1 Adverse events

8.1.1 Definitions and reporting

Adverse events that begin or worsen after informed consent should be recorded in the Adverse Events CRF. Conditions that were already present at the time of informed consent should be recorded in the Medical History page of the patient's CRF. Adverse event monitoring should be continued for at least 30 days (or 5 half-lives, whichever is longer) following the last dose of study treatment. Adverse events

(including lab abnormalities that constitute AEs) should be described using a diagnosis whenever possible, rather than individual underlying signs and symptoms. When a clear diagnosis cannot be identified, each sign or symptom should be reported as a separate Adverse Event.

The occurrence of adverse events should be sought by non-directive questioning of the patient at each visit during the study. Adverse events also may be detected when they are volunteered by the patient during or between visits or through physical examination, laboratory test, or other assessments. As far as possible, each adverse event should be evaluated to determine:

1. The severity grade (CTCAE Grade 1-4)
2. Its duration (Start and end dates or if continuing at the Safety Follow-up Visit)
3. Its relationship to the study treatment (Reasonable possibility that AE is related: No, Yes)
4. Action taken with respect to study or investigational treatment (none, dose adjusted, temporarily interrupted, permanently discontinued, hospitalized, unknown, not applicable)
5. Whether medication or therapy was given (no concomitant medication/non-drug therapy, concomitant medication/non-drug therapy)
6. Outcome (not recovered/not resolved, recovered/resolved, recovering/resolving, recovered/resolved with sequelae, fatal, unknown)
7. Whether it is serious, where a serious adverse event (SAE) is defined as in Section 8.2.1

All adverse events should be treated appropriately. Such treatment may include changes in study drug treatment including possible interruption or discontinuation, starting or stopping concomitant treatments, changes in the frequency or nature of assessments, hospitalization, or any other medically required intervention. Once an adverse event is detected, it should be followed until its resolution, and assessment should be made at each visit (or more frequently, if necessary) of any changes in severity, the suspected relationship to the study drug, the interventions required to treat it, and the outcome.

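### Section 6.2.2.5 bars giving the participant any biopsy result, with no stated exception for a malignant finding on either study core

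*Combined protocol and SAP*

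**What the plan says.** Section 6.2.2.5 describes a core biopsy of normal breast tissue, sent whole to research. Part is frozen and part is fixed for H & E and immunohistochemistry. On disclosure it has one sentence: "The patient will not receive any results of the biopsy". The section covers two biopsies, one before hydroxytyrosol and one after a year of it, and the sentence does not distinguish them. Note 9 to Table 7-1 makes the core mandatory for new patients.

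Section 6.2.2.8(a) lists as a ground for stopping treatment: "Evidence of any cancer at any time, including DCIS". It continues: "If the pathologic review of the baseline core needle breast biopsy confirms invasive breast cancer, the participant must be removed from protocol treatment".

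Two steps are then stated. Item (g) of the same list says: "All reasons for discontinuation of the intervention must be documented in the Off Treatment Notice". Section 6.2.2.9 adds: "Follow-up visits will continue even if the participant goes off study intervention early unless there is a withdrawal of consent".

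**The concern.** The non-disclosure sentence covers every result, not only the biomarker results that a research biopsy is meant to produce. The authors nevertheless foresaw that the same tissue might show cancer, and wrote a rule for that event. The rule deals with study treatment and does not mention telling the participant.

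What is at stake is participant safety. These women are enrolled because their breast cancer risk is raised, and the biopsy is a condition of entry for new patients. The whole specimen goes to research and no parallel clinical report is described, so the study reading may be the only one. Section 2.1, by contrast, separates the research reading of the mammograms from their clinical reading. Staff who followed 6.2.2.5 to the letter could stop the drug, complete the form and leave the woman unaware of a cancer.

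**Working it through.** The plan gives no figure to reproduce, so the check is a comparison of texts: does any available section lift the bar in 6.2.2.5?

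1. **Removal rule, 6.2.2.8(a).** It requires action on a malignant baseline core, but the action is to stop treatment. It neither requires nor forbids disclosure, so it can be obeyed together with 6.2.2.5.
2. **Review of baseline evaluations, 5.1.** The principal investigator or a designee must review the results of all baseline evaluations before enrollment. Table 7-1 lists the random core under prestudy evaluation. Together these make it probable that the investigator learns of a baseline finding. Neither speaks of the participant.
3. **Adverse events, 8.1.1.** Adverse events are to be treated appropriately, which would ordinarily mean informing the patient. But the section also says: "Conditions that were already present at the time of informed consent should be recorded in the Medical History page". Section 6.2.2 sets the order of events: "If the mammogram is read as normal or benign, participants will undergo a non-directed core needle biopsy within 30 days of signing consent". The baseline core thus comes shortly after consent, and a cancer seen on it could be classed as already present. This cover is indirect.
4. **Serious adverse events, 8.2.1 and 8.2.2.** A cancer first identified on a study core could qualify as medically significant. The reports go to the institution within 24 hours, and to the FDA and IRB. The participant is not among the recipients.
5. **Safety Criteria, section 5.** Abnormal findings are followed when they are believed to be treatment related. That cannot apply to a core taken before the first dose.
6. **Eligibility, 5.1 criteria 5 and 6.** The requirement for a negative or benign biopsy applies to women whose mammogram or BIRADS score raised suspicion. It does not concern the research core.
7. **The 12-month core.** Under 6.2.2.2 it is scheduled within 4 weeks of stopping the drug. Removal from treatment then has nothing to act on, and the pathology sentence in 6.2.2.8(a) names only the baseline core. Follow-up ends at 13 months. The adverse-event route fits better here, since a cancer could have arisen after consent, but it remains indirect.

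None of the seven lifts the bar.

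**Frequency.** The documents give no rate of malignant cores, so any figure is an assumption. Let p be the chance per woman of a malignant baseline core, and take the planned 100 women. Expected cases = 100 × p; chance of at least one = 1 − (1 − p)^100.

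- p = 0.01%: 0.01 expected; 1.0% chance of at least one.
- p = 0.1%: 0.1 expected; 9.5%.
- p = 0.5%: 0.5 expected; 39.4%.

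These values of p only illustrate the arithmetic and carry no weight in the conclusion. For baseline cores, 100 women is an upper bound: note 9 to Table 7-1 exempts patients already on the study, and 6.2.2.5 allows a substitute: "Breast tissue can be collected from a scheduled biopsy or surgery and used in place of the breast biopsy". In that case results would presumably come through usual care. The calculation leaves out the 12-month core.

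**The case against.** The strongest reply is that the sentence is being read too literally. It follows directly on a description of normal tissue sent to research, and its natural meaning is that routine research results are not returned. On that view 6.2.2.8(a) is the specific rule for the unexpected case, the investigator sees the baseline results, and section 8 leads to treatment. A woman can hardly be taken off treatment for cancer, or treated for it, without being told. Moreover, the consent pages and a block of text directly after 6.2.2.5 are missing from the reviewed copy, and an exception could stand in either.

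Much of this holds. A reader might infer that the protocol keeps a cancer finding from the physicians as well; 5.1, Table 7-1 and section 8 point the other way. A reader might also infer that 6.2.2.5 and 6.2.2.8(a) contradict each other, but both can be obeyed. Nor do the documents show an intention to hide a diagnosis: a treating physician would probably tell her. And because text is missing, it cannot be said that the full plan lacks an exception.

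What remains is narrower. The sentence says any results, and disclosure would rest on someone departing from it or reading it down. A protocol should expressly permit the right act.

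**Conclusion.** The point stands as a narrow safety correction to 6.2.2.5. In the available text the bar on giving the participant biopsy results has no exception, it covers both study cores, and the indirect routes through investigator review and adverse-event reporting do not remove it.

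The event should be rare, because the core is non-directed and the baseline core follows a mammogram read as normal or benign. How rare cannot be derived from the documents. The case for change rests on the seriousness of a single withheld cancer finding and the low cost of preventing it.

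The conclusion assumes that neither the consent form nor the missing text after 6.2.2.5 already provides for disclosure. A reader might infer a threat to the trial's results; there is none, since the primary endpoint is mammographic density and no endpoint, analysis or sample size changes.

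**What to change.** First check the consent form and the complete text following 6.2.2.5. If either already provides for disclosure of a malignant finding, add only a cross-reference in 6.2.2.5.

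Otherwise amend 6.2.2.5 to say that:

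- non-disclosure applies to research biomarker results;
- any malignant finding, invasive or DCIS, noted on the baseline or the 12-month study core is reported promptly to the participant and her treating physician.

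Cross-refer this to 6.2.2.8(a) and align the consent text.

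The cost is a minor consent alignment and a rare clinical notification. The change adds no pathology reading. Its limit follows from that: the available text does not say who reads the core or when, so the change secures disclosure of what is noted, not timely detection.
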